1 BACKGROUND INFORMATION

Introduction:

1.1 Background on the indication

PD-1 and CTLA-4 immune checkpoint inhibitors

Tumor antigen-specific T cells exposed to chronic antigenic stimulation develop an exhausted phenotype characterized by increased surface expression of various co-inhibitory checkpoint molecules (including PD-1, LAG-3, TIM-3, and others) and loss of effector function¹. Blockade of co-inhibitory checkpoint molecules can reinvigorate exhausted T cells and produce dramatic anti-tumor effects².

Over the past decade, treatment with immune checkpoint inhibitors has revolutionized the treatment of patients with advanced cancer. The combination of ipilimumab plus nivolumab has been shown to be one of the most effective treatment regimens for patients with advanced metastatic melanoma^{2,3}. Over half of patients with metastatic cutaneous melanoma treated with the combination of ipilimumab + nivolumab achieve at least a partial response and are alive 5 years later². The Checkmate 511 clinical trial showed that treatment with a reduced dose of ipilimumab (1 mg/kg) in combination with nivolumab (3 mg/kg) resulted in similar progression free survival and overall survival compared with lpilimumab 3 mg/kg + nivolumab 1 mg/kg. The lpi 1 mg/kg + Nivo 3 mg/kg regimen was far better tolerated with significantly less toxicity⁴.

Despite the success of immune checkpoint inhibitors and targeted therapeutics, melanoma continues to claim the lives of thousands each year. For patients with metastatic melanoma who are refractory to anti-PD-1 monotherapy, treatment with the combination of Ipilimumab plus nivolumab or pembrolizumab results in a median progression free survival of 3-5 months⁵⁻⁷. As such, improved therapy options for patients with PD-1 refractory cutaneous melanoma is a significant unmet clinical need.

Vascular endothelial growth factor (VEGF)

VEGF signaling within the tumor microenvironment results in profound local immunosuppression. VEGF signaling promotes tumor infiltration of regulatory T cells (Treg) and myeloid derived suppressor cells (MDSC) which suppress adaptive anti-tumor immune responses. VEGF signaling also inhibits dendritic cell maturation resulting in impaired antigen presentation and T cell activation⁸. Activated T cells upregulate VEGF cell surface receptors. VEGF signaling in activated T cells results in upregulated surface expression of co-inhibitory receptors as well as reduced cytotoxic activity and proliferative capacity^{9,10}.

CONFIDENTIAL - Cabozantinib + Nivolimab + Ipililumab Protocol Required Elements

Given that VEGF signaling has multiple pro-tumorigenic and immunosuppressive effects in cancer progression – there is a strong rationale for combining VEGF inhibition with immune checkpoint inhibition. Several recent clinical trials have demonstrated improved anti-tumor activity with combination therapies blocking VEGF and PD-1/PD-L1 signaling. We recently published the results of our phase Ib/II clinical trial with the combination of lenvatinib + pembrolizumab¹¹. This clinical trial showed impressive anti-tumor activity in heavily pre-treated patients including those with metastatic renal cell carcinoma and endometrial cancer¹².

1.2 Background on the compounds

Ipilimumab

Ipilimumab is a fully human IgG1 kappa monoclonal antibody that binds the co-inhibitory receptor CTLA-4. Antibody binding prevents interaction with the CTLA-4 ligands CD80 and CD86¹³. Blockade of CTLA-4 results in increased T cell activation and proliferation. Ipilimumab was the first immune checkpoint inhibitor to receive FDA approval as a cancer therapy. Treatment of patients with advanced metastatic melanoma with ipilimumab monotherapy resulted in improved overall survival¹⁴. Subsequent clinical trials with ipilimumab alone and in combination with anti-PD-1 antibodies have demonstrated impressive clinical activity in patients with melanoma, renal cell carcinoma, non-small cell lung cancer and other cancers^{2,15,16}. Side effects of ipilimumab result from autoimmune attack on healthy tissues. Side effects may include dermatitis, colitis, hepatitis, hypophysitis, pneumonitis, endocrinopathies, nephritis, arthritis, neuropathies and others.

Nivolumab

T cell activation results in upregulation of counter regulatory co-inhibitory receptors including PD-1 and CTLA-4. Ligation of these co-inhibitory receptors with their corresponding ligands results in diminished cytotoxicity and proliferative capacity. These regulatory mechanisms serve to prevent excessive immune activation and autoimmune disease. However, in some diseases such as cancer and chronic viral infections, chronic antigenic stimulation of T cells results in high expression of co-inhibitory checkpoint receptors which leads to T cell exhaustion. Nivolumab is a fully human IgG4 kappa monoclonal antibody that binds the co-inhibitory receptor PD-1. Nivolumab binding to PD-1 blocks interaction with the PD-1 ligands PD-L1 and PD-L2. PD-1 blockade can lead to reinvigoration of exhausted T cells and prevent T cell exhaustion of newly activated T cells. Nivolumab has been shown to have excellent clinical efficacy in treating a wide range of cancers as monotherapy and in combination with ipilimumab^{2,15,16}.

Cabozantinib

Cabozantinib is a potent small molecule inhibitor of multiple receptor tyrosine kinases. Cabozantinib inhibits VEGFR2, MER, KIT, and MET at single digit nanomolar IC_{50} concentrations. Other kinases including ROS1, RET, FLT3, RON, AXL, and TIE2 are also inhibited with nanomolar concentrations of cabozantinib. Cabozantinib has been shown to have clinical activity in a variety of solid tumors and has been approved by the FDA for treatment of medullary thyroid cancer, renal cell carcinoma and hepatocellular carcinoma¹⁷⁻¹⁹.

1.3 Rationale for the proposed study

In this clinical trial, we will evaluate the clinical efficacy and safety of the combination of VEGF inhibition (cabozantinib 40 mg/day) with immune checkpoint inhibition (ipilimumab 1 mg/kg + nivolumab 3 mg/kg) for patients with metastatic cutaneous melanoma who are refractory to anti-PD-1/PD-L1 therapy. The hypothesis is that concurrent blockade of distinct and inter-related signaling pathways (VEGF and co-inhibitory immune checkpoint pathways), will result in improved anti-tumor immune reactivity and clinical efficacy. Inhibition of VEGF signaling in the tumor microenvironment will increase CD8+ T cell infiltration, reduce infiltration of Treg and MDSC populations, and block the direct immunosuppressive effects of VEGF on activated T cells. Blockade of PD-1 and CTLA-4 immune checkpoint pathways will facilitate reinvigoration of exhausted T cells and allow expansion and activation of a broader repertoire of tumor antigen-specific T cells.

2 STUDY OBJECTIVES AND ENDPOINTS

Recent clinical trials have demonstrated median PFS as high as 5 months with the combination of low dose ipilimumab (1 mg/kg IV every 3 weeks) in combination with anti-PD-1 therapies in patients with anti-PD1 refractory cutaneous melanoma. As such, we will use the 5 month mPFS as the benchmark for the design of this clinical trial. In order to show a 4 month improvement in mPFS (with a power of 0.8 and a one-sided test given a type I error rate of 0.05), a total of 41 subjects would need to be enrolled. This signal seeking pilot study will initially enroll 25 subjects at our site (single institution) in less than 2 years. If this treatment combination results in a *mPFS of at least 8 months or an ORR of 45% or higher*, we will review these results with BMS and Exelixis and propose protocol and budget amendments to add 1-2 additional sites to expedite enrollment to a total of at least 41 subjects.

Primary Objective

The primary objective of this clinical trial is to evaluate the clinical efficacy and progression free survival of the triplet combination of ipilimumab + nivolumab + cabozantinib in patients with anti-PD-1/PD-L1 refractory metastatic cutaneous melanoma.

Secondary Objectives:

- Safety/Tolerability (CTCAE v5.0)
- Objective response rate (iRECIST)
- Overall survival
- Correlative translational studies (paired pre-treatment and day #15 on-treatment tumor biopsies for characterization of tumor infiltrating immune cell profiling and gene expression changes)

Primary endpoint:

Progression free survival will be defined as the time between the date of enrollment and the first date of documented progression (per iRECIST), as determined by the investigator, or death due to any cause, whichever occurs first. Cumulative incidence functions will be displayed and summarized for the median time to progression as well as percentage of patients without disease progression at 12, 18, and 24 months.

Secondary endpoints:

- 1. Objective response rate (iRECIST)
- 2. Duration of response
- 3. 6, 12 and 24 month progression free survival
- 4. 12 month overall survival
- 5. Incidence of grade ≥3 treatment related adverse events (CTCAE v5.0)
- 6. Correlative molecular profiling

STUDY DESIGN: This is a phase II, single arm, single institution clinical trial. Adults (age ≥18 years-old) with anti-PD-1 refractory, unresectable/metastatic cutaneous melanoma will be evaluated for eligibility. Eligible participants will be treated with the triplet combination of ipilimumab 1 mg/kg + nivolumab 3 mg/kg every 3 weeks for 4 cycles in addition to cabozantinib 40 mg/day. For cycles 5+, treatment will

consist of nivolumab 480 mg IV every 4 weeks in combination with cabozantinib 40 mg/day. The total duration of therapy will be 24 months.

- Ipilimumab 1 mg/kg + Nivolumab 3 mg/kg IV every 3 weeks + Cabozantinib 40 mg PO daily for 4 cycles followed by:
- Nivolumab 480 mg IV every 4 weeks + Cabozantinib 40 mg PO daily for up to 24 months

2.1 Study Treatment Discontinuation

Subjects may discontinue study treatment or withdraw their consent to participate in the study at any time without prejudice. The Investigator may withdraw a subject from study treatment or from the study if, in his or her clinical judgment, it is in the best interest of the subject or if the subject cannot comply with the protocol.

In addition, any of the following conditions requires discontinuation of the subject from study treatment:

- An AE or intercurrent illness that in the opinion of the Investigator warrants the subject's withdrawal from study treatment.
- The Investigator believes it is not in the best interest of the subject to continue on study.
- Specific conditions described in the Management of Adverse Events Section 5.4.
- Necessity for treatment with other anticancer treatment prohibited by protocol.
- Sexually active subjects who refuse to use medically accepted barrier methods of contraception
 (e.g., male condom, female condom) during the study and for 4 months after the last dose of
 cabozantinib and 3 months after the last dose of ipilimumab and 5 months after the last dose of
 nivolumab.
- Women who become pregnant or are breastfeeding.
- If the subject does not recover from his or her toxicities to tolerable Grade ≤ 2 within 6 weeks,
 the subject will have study treatment discontinued unless there is unequivocal evidence that the
 subject is benefitting. In this situation, a subject may be able to restart therapy with a dose
 reduction upon resolution of the toxicity and with agreement of the Principal Investigator.
- Necessity for interrupting all study treatment for greater than 12 weeks for study-treatmentrelated AEs unless approved by the Principal Investigator.

- Request by regulatory agencies for termination of treatment of an individual subject or all subjects under the protocol.
- Significant noncompliance with the protocol schedule in the opinion of the Investigator.
- Subjects who cannot tolerate the minimum protocol-specified dose of study treatment will have study treatment discontinued.
- Progressive disease (PD) or the subject no longer experiences clinical benefit as determined by the Investigator. Patients who continue study treatment beyond progression must be reconsented into the study.
- Subject participation in another clinical study using an investigational agent, investigational medical device, or other intervention.
- Subject request to discontinue all study treatments (with or without concurrent withdrawal of informed consent).

3 INCLUSION/EXCLUSION CRITERIA

3.1 Inclusion Criteria

To be eligible for the study, the subject must meet all of the inclusion and none of the exclusion criteria:

- 1. Histologically (or cytologically) confirmed diagnosis of metastatic cutaneous melanoma.
- 2. Prior therapy:
 - a. Must have been treated previously with an immune checkpoint inhibitor targeting PD-1 or PD-L1.
 - b. Disease progression following treatment with prior anti-PD-1/PD-L1 therapy must be confirmed at least 4 weeks after the first imaging showing disease progression to rule out pseudoprogression.
 - c. Prior therapy with BRAF/MEK inhibitors (before or after anti-PD-1(L1) therapy) is allowed but not required.
 - d. Patients who develop unresectable/metastatic disease **while** receiving or following completion of adjuvant systemic anti-PD-1/PD-L1 therapy are eligible.
- 3. Recovery to baseline or \leq Grade 1 CTCAE v5 from toxicities related to any prior treatments, unless AE(s) are clinically nonsignificant and/or stable on supportive therapy.
- 4. Men and women, aged ≥ 18 years
- 5. Measurable disease meeting the following iRECIST criteria:
 - a. At least 1 lesion of ≥1.0 cm in the longest diameter for a non-lymph node or >1.5 cm in the short-axis diameter for a lymph node metastasis that is serially measurable according to

CONFIDENTIAL - Cabozantinib + Nivolimab + Ipililumab Protocol Required Elements

- iRECIST using computed tomography/magnetic resonance imaging (CT/MRI).
- b. Lesions that have had external beam radiotherapy must show evidence of disease progression to qualify as a target lesion.
- 6. ECOG performance status ≤ 1
- 7. Adequate cardiac function, as defined by:
 - a. Left ventricular ejection fraction (LVEF) ≥ 50% as determined by a multigated acquisition (MUGA) scan or echocardiogram,
 - b. Baseline QTc interval ≤ 480 ms
- 8. Adequate organ and marrow function, based upon meeting all of the following laboratory criteria within 14 days before first dose of study treatment:
 - a. Absolute neutrophil count (ANC) ≥ 1500/μL without granulocyte colony-stimulating factor support.
 - b. White blood cell count $\geq 2500/\mu L$.
 - c. Platelets \geq 100, 000/ μ L without transfusion.
 - d. Hemoglobin \geq 9 g/dL (\geq 90 g/L).
 - e. Alanine aminotransferase (ALT), aspartate aminotransferase (AST), and alkaline phosphatase (ALP) ≤ 3x upper limit of normal (ULN). ALP ≤ 5x ULN with documented bone metastases.
 - f. Total bilirubin \leq 1.5 x ULN. Note: Individuals who have a total bilirubin level >1.5 X ULN will be allowed if their indirect bilirubin level is < 1.5 x ULN (i.e., participants with suspected or known diagnosis of Gilbert's Syndrome)
 - g. Serum albumin ≥ 2.8 g/dl.
 - h. (PT)/INR or partial thromboplastin time (PTT) test < 1.3x the laboratory ULN
 - i. Serum creatinine ≤ 1.5x ULN or calculated creatinine clearance ≥ 40mL/min
 (≥ 0.675mL/sec) using the Cockcroft-Gault equation:
 - Males: $(140 age) \times (kg)/(serum creatinine [mg/dL] \times 72)$
 - Females: $[(140 age) \times weight (kg)/(serum creatinine [mg/dL] \times 72)] \times 0.85$
 - j. Urine protein/creatinine ratio (UPCR) \leq 1 mg/mg (\leq 113.2 mg/mmol), or 24-h urine protein \leq 1 g.
- 9. Capable of understanding and complying with the protocol requirements and must have signed the informed consent document.
- 10. Sexually active fertile subjects and their partners must agree to use medically accepted methods of contraception (e.g., barrier methods, including male condom, female condom, or diaphragm with spermicidal gel) during the course of the study and for 4 months after the last dose of

- cabozantinib and 3 months after the last dose of ipilimumab and 5 months after the last dose of nivolumab.
- 11. Participants of childbearing potential must have a negative serum or urine pregnancy test (minimum sensitivity 25 IU/L or equivalent units of human chorionic gonadotropin [HCG]) at screening, within 24 hours prior to receiving the first dose of study medication, and then every 4 weeks while on treatment.
- 12. Participants of child-bearing potential agree to use highly effective methods of contraception starting with the first dose of assigned study intervention through 5 months after the last dose of study therapy. Participants of childbearing potential are those who are not proven postmenopausal. Postmenopausal is defined as any of the following:
 - a. Amenorrheic for 1 year or more following cessation of exogenous hormonal treatments
 - b. Luteinizing hormone (LH) and Follicle stimulating hormone (FSH) levels in the postmenopausal range for women under 50
 - c. Radiation-induced oophorectomy with last menses >1 year ago
 - d. Chemotherapy-induced menopause with >1 year interval since last menses
 - e. Surgical sterilisation (bilateral oophorectomy or hysterectomy

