4.1.1 Clinical Safety Laboratory Assessments

Clinical Safety Laboratory Assessments		
Hematology – CBC with Hemoglobin, Hematocrit, Total leukocyte count, including differential and		
Platelet count		
Chamistry		
Chemistry		
Aspartate aminotransferase (AST)	Albumin	
Alanine aminotransferase (ALT)	Sodium	
Total bilirubin Potassium		
Alkaline phosphatase (ALP)	Chloride	

Lactate dehydrogenase (LDH)	Calcium
Creatinine	Phosphorus
Blood Urea Nitrogen (BUN) or serum UREA	СК
Glucose	GGT- screening
Bicarbonate	Magnesium-screening
Total Protein	Troponin - screening
	TSH, and free T4 - screening
	TSH, with reflexive fT4 if TSH is
	abnormal - on treatment
	Lipase and /or amylase
	•

PT/INR/PTT, and drug adherence checks

Serology

Hepatitis B/C, (HBV sAG, HCV antibody or HCV RNA), - screening only

(Testing for HIV-1 and HIV-2 must be performed where mandated by local requirements)

Other Analyses

Serum Pregnancy test (WOCBP only: minimum sensitivity 25 IU/L or equivalent units of HCG).

Follicle stimulating hormone (FSH) screening -only required to confirm menopause in women < age 55)

Urinalysis with UPCR (urine protein creatinine ratio) - screening and at each study visit

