- Grade 3 drug-related endocrinopathies, adequately controlled with only physiologic hormone replacement;
- Grade 4 neutropenia ≤ 7 days;
- Grade 4 lymphopenia or leukopenia;
- Isolated Grade 4 electrolyte imbalances/abnormalities that are not associated with clinical sequelae and are corrected with supplementation/appropriate management within 72 hours of their onset;
- Grade 4 drug-related endocrinopathy AEs, such as, hyper- or hypothyroidism, or glucose
 intolerance, which resolve or are adequately controlled with physiologic hormone replacement
 (corticosteroids, thyroid hormones) or glucose-controlling agents, respectively, may not require
 discontinuation after discussion with and approval from the Principal Investigator;
- Dosing delays to allow for prolonged steroid tapers to manage drug-related adverse events are allowed. Drug-related adverse events are any toxicity temporally associated with administration of the investigational agent that may be at least possibly related to study treatment;

 Dosing delays lasting > 12 weeks from the previous dose that occur for non-drug-related reasons may be allowed if approved by the Principal Investigator.

Prior to re-initiating treatment in a participant with a dosing delay lasting > 12 weeks, the Principal Investigator must be consulted. Tumor assessments should continue as per protocol even if dosing is delayed. Periodic study visits to assess safety and laboratory studies should also continue as clinically indicated during such dosing delays.

5.4.3 Management of Hepatocellular Toxicity Associated with Cabozantinib and Nivolumab and Ipililumab

Elevations of aminotransferases (ALT and AST) and bilirubin have been observed during treatment with cabozantinib, anti-PD-(L)1 agents, and anti-CTLA-4 agents. It is recommended that subjects with elevation of ALT, AST, and/or bilirubin have more frequent laboratory monitoring of these parameters. If possible, hepatotoxic concomitant medications should be discontinued in subjects who develop increased values of ALT, AST, or bilirubin, and other causes (e.g., cancer-related, infection) should be evaluated.

The following condition requires discontinuation of all study drugs:

 Drug-related ALT or AST > 3x ULN in combination with total bilirubin > 2x ULN without reasonable other explanation, consistent with drug-induced liver injury (DILI).

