AST or ALT > 3 - ≤ 5 x ULN or total bili > 1.5 - ≤ 3x ULN	 Cabozantinib: Interrupt cabozantinib dosing. If LFTs return to baseline grade, resume cabozantinib at a reduced dose. After completion of ipililumab, re-escalate cabozantinib dose as per protocol. If no additional ipililumab doses are to be administered, the dose of cabozantinib may be re-escalated no sooner than 10 days after re-initiation of cabozantinib. See above section for additional guidance. Nivolimab/Ipilulimab: Delay therapy per protocol. If LFTs return to baseline grade, resume therapy per protocol. 	 Monitor LFTs twice weekly or more frequently as deemed clinically necessary. If tapering off steroid therapy, monitor LFTs once weekly or more often per clinical judgment^b. If LFTs return to baseline grade, resume with routine monitoring. If LFT elevations persist > 3 days or worsen: Administer 0.5-1 mg/kg/day methylprednisolone or oral equivalent. When LFTs return to baseline grade or CTCAE Grade ≤1, taper steroids over at least 1 month^b. Consider prophylactic antibiotics for opportunistic infections.
AST or ALT > 5x ULN or total bili > 3x ULN or as otherwise specified	 Cabozantinib: Discontinue cabozantinib if ALT or AST > 8x ULN. Otherwise interrupt cabozantinib dosing and resume at a reduced dose after LFTs return to baseline grade (Sponsor approval required) Nivolimab/Ipilulimab: Discontinue therapy for Grade 3 ALT/AST, unless the Investigator in consultation with the Principal Investigator determines a favorable risk/benefit ratio that warrants continuation of both Nivolumab and Ipililumab or of Nivolumab alone 	 Monitor LFTs twice weekly or more frequently as deemed clinically necessary. During steroid taper, monitor LFTs once weekly or more often per clinical judgment^b. For Grade 3: Administer 1.0-2.0 mg/kg/day methylprednisolone IV or IV equivalent. For Grade 4: Administer 2.0 mg/kg/day methylprednisolone IV or IV equivalent. Add prophylactic antibiotics for opportunistic infections. Consult Gastroenterologist. When LFTs return to baseline grade or Grade 2, taper steroids over at least 1 month^b.

		 If LFT elevations do not improve in > 3 days, worsen or rebound: Add mycophenolate mofetil 1g BID. If no response within an additional 3-5 days, consider other immune-suppressants per local guidelines.

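### Inclusion criterion 8f contradicts itself: its bilirubin exception admits mainly direct rises and bars nearly all isolated indirect rises, although it names Gilbert's syndrome as the group it is for

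*Combined protocol and SAP*

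**What the plan says.** Section 3.1, criterion 8f, sets total bilirubin at no more than 1.5 x ULN within 14 days before the first dose. A note then makes an exception. It applies to "Individuals who have a total bilirubin level >1.5 X ULN", who "will be allowed if their indirect bilirubin level is < 1.5 x ULN". A parenthesis in the same sentence explains who these people are: "i.e., participants with suspected or known diagnosis of Gilbert's Syndrome".

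No other section restates or corrects this rule. The laboratory table in Section 4.1.1 lists total bilirubin and neither fraction, so the quantity on which the exception turns is not in the listed panel.

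The hepatotoxicity table in Section 5.4.3 is written in total bilirubin. Its second row begins where the exception begins: "AST or ALT > 3 - ≤ 5 x ULN or total bili > 1.5 - ≤ 3x ULN".

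**The concern.** The sentence has two halves, a numeric test and a named group. They should select the same patients, but they point in opposite directions. A patient whose total is high while the indirect fraction is held down has, in the main, a raised direct fraction. Gilbert's syndrome is a rise of the indirect fraction. The documents do not state that last fact; it is general medical knowledge and is used here as an assumption.

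Eligibility is at stake in two ways:

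- If site staff follow the number, patients with a direct rise can satisfy 8f whatever their total, in a trial of drugs for which Section 5.4.3 reports aminotransferase and bilirubin elevations.
- If site staff follow the named group, they enrol patients who fail the number, which is an eligibility deviation.

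Two coordinators could read the same laboratory report and reach opposite decisions.

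**Working it through.** The plan gives no figure to reproduce, so the check is one of logic, illustrated with numbers. Write T, D and I for total, direct and indirect bilirubin, with T = D + I, and U_T, U_D and U_I for their upper limits of normal. The documents give no ULN values; those below are assumptions.

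**Inputs from 8f.** The exception applies when T > 1.5 U_T and is granted when I < 1.5 U_I.

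**Case A: the limits add up, U_T = U_D + U_I.**

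- Everyone admitted has D = T − I > 1.5 U_T − 1.5 U_I = 1.5 U_D. So every admitted patient has direct bilirubin above 1.5 times its own limit.
- Take an isolated indirect rise, D ≤ U_D with T > 1.5 U_T. Then I = T − D > 1.5 U_T − U_D = 1.5 U_I + 0.5 U_D, which exceeds 1.5 U_I. Every such patient is refused.
- Take an isolated direct rise, I ≤ U_I with T > 1.5 U_T. Then I < 1.5 U_I. Every such patient is accepted, however high T is.

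**Case B: the total's limit is also used for the indirect fraction, U_I = U_T.** With U_T = 1.2 mg/dL and U_D = 0.3 mg/dL, both cut-offs are 1.5 × 1.2 = 1.80. An isolated indirect rise now passes if I < 1.80 and D ≤ 0.30 while D + I > 1.80. That confines I to between 1.50 and 1.80, and T to between 1.80 and 2.10 (1.5 to 1.75 x ULN). For example, T = 1.90 with I = 1.75 and D = 0.15 is admitted, although the rise is indirect. Beyond that narrow band, isolated indirect rises are still refused.

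**Grid check.** D and I each ran from 0 to 5 mg/dL in steps of 0.05, keeping points with T > 1.5 U_T.

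| Assumed ULN, total/direct/indirect (mg/dL) | Isolated indirect rises admitted | Isolated direct rises admitted |
|---|---|---|
| 1.2 / 0.3 / 0.9 | 0 of 469 | 1387 of 1387 |
| 1.0 / 0.3 / 0.7 | 0 of 511 | 1155 of 1155 |
| 1.2 / 0.4 / 0.8 | 0 of 612 | 1224 of 1224 |
| 1.2 / 0.3 / 1.2 (Case B) | 15 of 469 | 1900 of 1900 |

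These counts show the direction of the rule. They are not patient frequencies.

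**Single patients at 1.2/0.3/0.9** (cut-offs: total 1.80, indirect 1.5 × 0.9 = 1.35):

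- T = 2.5, I = 2.3, D = 0.2: 2.3 is not below 1.35, so refused. This is the isolated indirect pattern.
- T = 2.5, I = 0.5, D = 2.0: 0.5 is below 1.35, so allowed.
- T = 6.0, I = 1.0, D = 5.0: 1.0 is below 1.35, so allowed under 8f at 6.0/1.2 = 5 x ULN.

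**The other reading.** If the parenthesis is a further condition, a patient must have Gilbert's syndrome and also I < 1.5 U_I. In Case A no isolated indirect rise meets both; in Case B only the borderline band does. The exception is then almost empty.

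**The case against.** Four objections deserve an answer.

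*The logic is not strict.* Correct in part. It is strict only when the fractions' limits add up to the total's limit. With one shared limit the borderline band passes, so the fair wording is mainly direct and nearly all indirect.

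*The parenthesis may restrict entry.* On that reading, a patient with an unexplained direct rise and no Gilbert's syndrome is not admitted. This removes the safety worry, but the exception then shuts out the group it names. Neither reading works.

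*Other criteria stand in the way.* A reader might infer that any patient with a direct rise would enter. The documents do not support that, because all criteria must be met together. Section 3.1 limits ALT, AST and ALP to 3 x ULN (5 x ULN for ALP with bone metastases), requires albumin of at least 2.8 g/dL and limits INR or PTT. Section 3.2 excludes symptomatic cholangitis and acute common bile duct obstruction (no. 20) and Child-Pugh B or C (no. 27), and leaves room for investigator judgment (no. 10). These remove some direct-rise patients, not all, and none of them helps a patient with Gilbert's syndrome who has been refused. The absence of a cap on total is therefore a statement about 8f alone.

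*Clash with Section 5.4.3.* A reader might also infer that exception patients must have treatment interrupted or delayed on day 1, and that their liver data could not be interpreted. The documents do not support either inference. The table is suggested guidance for hepatotoxicity related to study treatment; the delay criterion in Section 5.4.2.1 concerns drug-related abnormalities; and resumption is judged against the baseline grade, so an abnormal baseline is foreseen. Any exception above 1.5 x ULN would overlap the table's rows, whichever fraction is limited. What remains is that the protocol does not say how such patients are to be read against those rows.

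**Conclusion.** Criterion 8f is inconsistent as written and needs correction. Its numeric test admits mainly direct rises, without an upper limit on total under 8f alone, and refuses nearly all isolated indirect rises, while its own explanation names an indirect condition. Read with the explanation as a restriction, it admits almost nobody.

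The conclusion rests on total being the sum of the two fractions and on Gilbert's syndrome being an indirect hyperbilirubinaemia. The strict form also needs the limits to add up; without that, only the borderline band changes. The documents give no count of affected patients. Few are likely, and there is no effect on sample size, power or type I error. The point matters for eligibility and patient safety.

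**What to change.** By amendment, the sponsor should:

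1. Reconcile the bilirubin fraction limited in 8f with the group named in the same sentence, and say whether that group is an illustration or a condition of entry.
2. Add the fraction that the reconciled rule needs to the screening entries of the laboratory table in Section 4.1.1, and state which ULN applies to it.
3. State how patients admitted under the exception relate to the total-bilirubin rows of Section 5.4.3.

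Which fraction and which limit are for the sponsor to settle; none is proposed here. The cost is a short text amendment through the approvals in Section 11, plus a fractionated bilirubin result for patients considered under the exception. The effect on accrual cannot be estimated from the documents.
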